9.3 Safety Endpoint

The primary clinical endpoint is the frequency of ZIKV-related AEs, as classified by both severity and seriousness, through active and passive surveillance. Separate assessments of systemic and local reactions will be performed.

9.4 Immunogenicity

ZIKV neutralizing antibody titers will be measured on Study Days 0, 28, 56, 90, and 180. Seroconversion to ZIKV will be defined as a PRNT₅₀ of $\geq 1:10$ based on a pre-inoculation PRNT₅₀ of $<1:5$ (seronegative to ZIKV).

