2. Seven subjects from cohort 3 and 7 subjects from cohort 4 will be selected for mosquito-feeding. They will also be randomized 5:2 (ZIKV:placebo) to ensure the clinical team remains blinded to the treatment assignment.

Product Description: ZIKV-SJRP/2016-184 and ZIKV-Nicaragua/2016 were isolated directly from the serum of subjects who were diagnosed with uncomplicated Zika illness. Each virus will first be evaluated at a dose of 10² plaque-forming units (PFU). At each subcutaneous dose, the virus will first be evaluated in 7 subjects (5 will have received ZIKV, 2 will have received placebo). The remaining subjects in each dose cohort will be inoculated with the current dose or dose escalation will occur according to predetermined criteria.

Primary Study Objective: Identify a suitable strain of ZIKV for use in safety-assured CHIM studies by:

1. Determining the proportion of infected subjects who demonstrate clinical signs/symptoms of Zika infection (fever, rash, conjunctivitis, pruritis, myalgia, arthralgia, headache) by ZIKV strain and dose
2. Determining the quantity and duration of ZIKV in blood, urine, cervico-vaginal secretions, semen, and saliva by culture (infectious virus) and by reverse transcriptase – polymerase chain reaction (RT-PCR)
3. Determining if dose correlates with incidence/duration of ZIKV in blood, urine, cervico-vaginal secretions, semen, and saliva

A suitable ZIKV strain for CHIM studies is defined as one in which:

1. $\geq 80\%$ of ZIKV or DENV-naïve inoculated subjects develop detectable viremia, as determined by direct virus culture **and**
2. Infectious virus is detected on more than 1 day for $\geq 80\%$ of subjects with detectable viremia **and**
3. The geometric mean peak titer of virus recovered by culture is $2.0 - 3.0 \log_{10}$ PFU/mL

Ideally, the ZIKV strain would also induce one or more of the following clinical signs in $\geq 50\%$ of infected subjects, however this will not be included in dose escalation criteria.

- a) Fever
- b) Rash
- c) Non-purulent conjunctivitis
- d) Myalgia
- e) Arthralgia

Secondary Study Objectives:

1. Characterize the clinical presentation of acute ZIKV infection by assessing the frequency of adverse events (AEs), graded by severity, occurring within 28 days of ZIKV administration
2. Longitudinal analysis of virus present in blood, urine, saliva, cervico-vaginal secretions, and semen
3. Time course of the neutralizing antibody response to ZIKV infection

Exploratory Objectives:

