2.2 Secondary Objectives

- Characterize the clinical presentation of acute ZIKV infection by assessing the frequency of adverse events (AEs), graded by severity, occurring within 28 days of ZIKV administration.
- Determine the quantity and duration of ZIKV presence as determined by:
 - The peak virus titer in the blood and the duration of viremia induced by the ZIKV strain at each tested dose as determined by RT-PCR and virus culture
 - The quantity and duration of ZIKV shedding in saliva determined by RT-PCR and virus culture
 - The quantity and duration of ZIKV shedding in urine determined by RT-PCR and virus culture
 - The quantity and duration of ZIKV shedding in cervico-vaginal secretions determined by RT-PCR and virus culture
 - The quantity and duration of ZIKV shedding in semen determined by RT-PCR and virus culture
- Evaluate the kinetics of the serum neutralizing antibody response following primary ZIKV infection and determine the peak neutralizing antibody response to ZIKV through Study Day 90.

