3. Obtain approximately 15 mL of blood for virus isolation from serum and whole blood (PCR and culture) and PAXGene.

Study Day 2

1. Perform interim history and focused physical exam, concentrating on any acute complaints.
2. Record vital signs twice a day.
3. Obtain approximately 15 mL of blood for virus isolation from serum and whole blood (PCR and culture).
4. Obtain clean-catch urine for virus isolation (PCR/culture).
5. Obtain saliva sample for virus isolation (PCR/culture).
6. Obtain 2 mL of blood for PAXGene.

Study Day 3

1. Perform interim history and focused physical exam, concentrating on any acute complaints.
2. Record vital signs twice a day.
3. Obtain approximately 15 mL of blood for virus isolation from serum and whole blood (PCR and culture) and PAXGene.

Study Day 4

1. Perform interim history and focused physical exam, concentrating on any acute complaints.
2. Record vital signs twice a day.

3. Obtain approximately 47 mL of blood for CBC with differential, virus isolation from serum and whole blood (PCR/culture), immunology (serum, plasma, PBMCs), and PAXGene.
4. Obtain clean-catch urine for virus isolation (PCR/culture).
5. Obtain cervico-vaginal secretion or semen sample for virus isolation (PCR/culture).
6. Obtain saliva sample for virus isolation (culture/PCR).
7. Obtain oral fluid for serology (CIR site only).

Study Day 5

1. Perform interim history and focused physical exam, concentrating on any acute complaints.
2. Record vital signs twice a day.
3. Obtain 13 mL of blood for virus isolation from serum and whole blood (PCR/culture).
4. Cohorts 3 and 4: Perform mosquito feeding on subset of volunteers.

Study Day 6

1. Perform interim history and focused physical exam, concentrating on any acute complaints.
2. Record vital signs twice a day.
3. Obtain approximately 15 mL of blood for virus isolation from serum and whole blood (culture/PCR) and PAXGene.
4. Obtain clean-catch urine for virus isolation (PCR/culture).
5. Obtain saliva sample for virus isolation (PCR/culture).
6. Obtain oral fluid for serology (CIR site only).
7. Cohorts 3 and 4: Perform mosquito feeding on subset of volunteers.

Study Day 7

1. Perform interim history and focused physical exam, concentrating on any acute complaints.
2. Record vital signs twice a day.
3. Obtain 13 mL of blood for virus isolation from serum and whole blood (PCR/culture).
4. Cohorts 3 and 4: Perform mosquito feeding on subset of volunteers.

Study Day 8

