3. Obtain approximately 22 mL of blood for CBC with differential, AST, ALT, serum creatinine, virus isolation from serum and whole blood (PCR/culture), and PAXGene.

4. Obtain clean-catch urine for virus isolation (PCR/culture).
5. Obtain cervico-vaginal secretion or semen sample for virus isolation (PCR/culture).
6. Obtain saliva sample for virus isolation (PCR/culture).
7. Obtain oral fluid for serology (CIR site only).
8. Perform serum β -HCG testing (females only).
9. Review pregnancy prevention and continued use of barrier contraceptives.

Study Day 14 (\pm 1 day from 14 days following test article administration)

1. Perform interim history, including sexual history, and focused physical exam, concentrating on any acute complaints.
2. Record vital signs from subject diary card and perform vital signs.
3. Obtain approximately 45 mL of blood for immunology (serum, plasma, PBMCs), PAXGene, and virus isolation from serum and whole blood (PCR/culture).
4. Obtain clean-catch urine for virus isolation (PCR/culture).
5. Obtain cervico-vaginal secretion sample for virus isolation (PCR/culture).
6. Obtain saliva sample for virus isolation (PCR/culture).
7. Obtain oral fluid for serology (CIR site only).
8. Perform serum β -HCG testing (females only).
9. Review pregnancy prevention and continued use of barrier contraceptives.

Study Day 16 (\pm 1 day from 16 days following test article administration)

1. Perform interim history, including sexual history, and focused physical exam, concentrating on any acute complaints.
2. Record vital signs from subject diary card and perform vital signs.
3. Obtain approximately 22 mL of blood for CBC with differential, AST, ALT, serum creatinine, virus isolation from serum and whole blood (PCR/culture), and PAXGene.
4. Perform serum β -HCG testing (females only).
5. Obtain clean-catch urine for virus isolation (PCR/culture).
6. Obtain cervico-vaginal secretion or semen sample for virus isolation (PCR/culture). (Cervico-vaginal cup may be inserted at home by the volunteer prior to presentation to the clinic).
7. Obtain saliva sample for virus isolation (PCR/culture).
8. Obtain oral fluid for serology (CIR site only).
9. Review pregnancy prevention and continued use of barrier contraceptives.

Study Day 21 (\pm 1 day from 21 days following test article administration)

1. Perform interim history, including sexual history, and focused physical exam, concentrating on any acute complaints.

2. Record vital signs.

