3. Perform serum β -HCG testing (females only).
4. Review pregnancy prevention and continued use of barrier contraceptives with all subjects.
5. Obtain approximately 40 mL of blood for immunology (serum, plasma, PBMCs), PAXGene and virology* from serum and whole blood (PCR/culture). CBC will be done if prior white blood cell count (WBC), ANC, platelet count, or hemoglobin results are a Grade I or above and unresolved, as defined by protocol, on Study Day 16.
6. Obtain clean-catch urine for virus isolation (PCR/culture).
7. Obtain cervico-vaginal secretion or semen sample for virus isolation (PCR/culture). (Cervico-vaginal cup may be inserted at home by the volunteer prior to presentation to the clinic).
8. Obtain saliva sample for virus isolation (PCR/culture).
9. Obtain oral fluid for serology (CIR site only).
10. Review pregnancy prevention and continued use of barrier contraceptives.

*Whole blood/serum virology will be done only for those subjects who had detectable ZIKV in the blood at Study Day 16.

Study Day 28 (\pm 2 days from 28 days following test article administration)

1. Perform interim history, including sexual history, and focused physical exam, concentrating on any acute complaints.
2. Record vital signs.
3. Obtain approximately 50 mL of blood for immunology (serum, plasma, PBMCs), PAXGene and virology* from serum and whole blood (PCR/culture).
4. Obtain clean-catch urine for virus isolation* (PCR/culture).
5. Obtain cervico-vaginal secretion or semen sample for virus isolation* (PCR/culture). (Cervico-vaginal cup may be inserted at home by the volunteer prior to presentation to the clinic).
6. Obtain saliva sample for virus isolation* (PCR/culture).
7. Obtain oral fluid for serology (CIR site only).
8. Perform serum β -HCG testing (females only).
9. Review pregnancy prevention and continued use of barrier contraceptives.

*Whole blood/serum/CSV/semens/saliva/urine virology will be done only for those subjects who had detectable ZIKV in the blood at Study Day 21.

Study Day 35 (\pm 2 days from 35 days following test article administration)

1. Perform interim history, including sexual history, and focused physical exam, concentrating on any acute complaints.

2. Record vital signs.
3. Collect 8 mL blood for whole blood/serum virus isolation* (PCR/culture). Assays will be performed only for those subjects who had detectable ZIKV in the blood at Study Day 28.
4. Obtain clean-catch urine for virus isolation* (PCR/culture).

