9.5.3 Immunogenicity Data

The frequency of seroconversion and peak neutralizing antibody titers will be included in the per-protocol analysis for all subjects who were enrolled through Study Day 90 and have samples from at least 2 of the following 3 time-points (Day 28, 56, 90).

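### With no neutralizing titer between Day 0 and Day 28, the kinetics objective cannot show onset, early slope or time of seroconversion, although serum from Days 14 and 21 is already drawn

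*Combined protocol and SAP*

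**What the plan says.** The objective appears twice. The precis lists among the secondary objectives "Time course of the neutralizing antibody response to ZIKV infection". Section 2.2 is more specific: "Evaluate the kinetics of the serum neutralizing antibody response following primary ZIKV infection", and also "determine the peak neutralizing antibody response to ZIKV through Study Day 90".

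The assay days are in Section 9.4: "ZIKV neutralizing antibody titers will be measured on Study Days 0, 28, 56, 90, and 180". The same section defines seroconversion as a PRNT50 of at least 1:10 from a pre-inoculation value below 1:5.

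The analysis sets use the same days. Section 9.5.3 admits a subject to the per-protocol analysis of seroconversion and peak titer with samples from "at least 2 of the following 3 time-points (Day 28, 56, 90". Section 9.6.2 admits to the intent-to-treat analysis a subject who missed Day 90 but completed Day 28 or Day 56.

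Section 6.4.1.2 draws immunology serum well before Day 28. For Day 14 it says "Obtain approximately 45 mL of blood for immunology (serum, plasma, PBMCs), PAXGene, and virus isolation from serum and whole blood (PCR/culture", and for Day 21 "Obtain approximately 40 mL of blood for immunology (serum, plasma, PBMCs), PAXGene and virology* from serum and whole blood (PCR/culture". Days 4 and 8 also include immunology serum. Section 6.8.1 names the plaque reduction assay without giving days, and Table 1 has a serology row with collections before Day 28. Nothing in the documents assigns a neutralization assay to those samples.

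**The concern.** A kinetics or time-course objective asks when the response starts, how fast it climbs, how high it goes and how it then changes. The listed days give one baseline value and then nothing for four weeks. Everything about the early response is reduced to the difference between Day 0 and Day 28, and seroconversion can be dated only as having occurred by Day 28. The peak through Day 90 is the largest of three values, so a subject whose titer was highest before Day 28 would have that peak missed.

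What is at stake is one descriptive secondary objective. It still deserves attention because Section 9.2 counts describing each individual's immune response at multiple timepoints among the primary analyses, and because the samples that would fill the gap are already being taken.

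**Working it through.** No stated sample size, power or alpha bears on this point, so there is no plan figure to reproduce. The check counts time points on nominal study days.

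**Inputs.** Titer days are from Section 9.4, immunology serum days from Section 6.4.1.2, and virus timing in serum from Tables 5 and 7. Table 7 shows one more value per row than its column headings explain; I read the extra value as the maximum titer, which makes onset 3.0 days and duration 5.4 days for culture, and 2.4 and 11.4 days for PCR.

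**Step 1: titer points and gaps.**

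| Schedule | Titers after Day 0 and before Day 28 | Titers after Day 0 through Day 90 | Gaps through Day 90 (days) |
|---|---|---|---|
| Section 9.4 as written | 0 | 3 | 28, 28, 34 |
| Adding Days 14 and 21 | 2 | 5 | 14, 7, 7, 28, 34 |
| Adding Days 4, 8, 14 and 21 | 4 | 7 | 4, 4, 6, 7, 7, 28, 34 |

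The time of seroconversion is known only to within the gap in which it falls. For a subject positive at Day 28 that gap is 28 − 0 = 28 days as planned. With Days 14 and 21 added it is at most 14 days.

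**Step 2: where the gap sits relative to infection.** Mean end of virus in serum = mean onset + mean duration.

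- SJRP, culture: 4.0 + 4.7 = Day 8.7, which is 19.3 days before Day 28.
- Nicaragua, culture: 3.0 + 5.4 = Day 8.4, which is 19.6 days before Day 28.
- SJRP, PCR: 2.5 + 7.5 = Day 10.0, which is 18.0 days before Day 28.
- Nicaragua, PCR: 2.4 + 11.4 = Day 13.8, which is 14.2 days before Day 28.

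The culture results agree with the precis statement that infectious virus left the blood before Day 9. The first post-inoculation titer therefore comes about 14 to 20 days after mean clearance from serum.

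**Step 3: how much a missed peak could matter (assumed values only).** If titer falls exponentially after its peak, then Day 28 titer / true peak = 2^(−(28 − peak day) / half-life). The documents give neither the peak day nor the half-life, so both are varied.

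| Assumed peak day | Half-life 7 d | 14 d | 30 d | 60 d |
|---|---|---|---|---|
| 14 | 25% | 50% | 72% | 85% |
| 21 | 50% | 71% | 85% | 92% |

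If titers peak at or after Day 28, Days 14 and 21 add nothing to the estimate of the peak.

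**Step 4: workload.** 56 subjects × 2 days = 112 assays. Of these, 28 × 2 = 56 would be on stored serum from cohorts 1 and 2. Adding Day 8 for everyone would be 56 more.

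**The case against.** The strongest reply is that the trial is declared exploratory and that four post-inoculation titers over six months already describe a time course, though a coarse one. Nothing that drives decisions depends on early titers: strain suitability, enrolment of the second block of seven and the halting rules do not use them. Seroconversion is needed only by Day 90. All specimens are stored (Section 8.3), and Section 6.8.1 leaves room for other neutralization assays, so early titers could be obtained later. These points stand, and they keep the matter small. They do not answer it, because titers before Day 28 have no place in Section 9.4 or in the analysis rules of 9.5.3 and 9.6.2.

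Four stronger readings are tempting, and the documents do not support them.

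- *The plan cannot show a rise.* It can: Day 0 against Day 28 shows that a rise occurred and its net size.
- *The reported peak is biased low.* This would be so only in a subject who peaks before Day 28. No section says when titers peak, and the percentages above rest on assumed values.
- *The trial loses its ability to relate antibody to viral clearance or semen shedding.* Neither relation is a listed objective. Semen is also collected on Days 28, 56 and 90, which are titer days, although assays at those visits are conditional.
- *Adding Days 14 and 21 would cover the viremic period.* Onset through culture clearance, at about Day 8, would still fall between the Day 0 and Day 14 titers. Only an earlier sample such as Day 8 would help there.

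Requiring a Day 21 or Day 28 sample before a subject counts toward the peak may also seem natural. With 10 virus recipients per cohort, it could remove subjects for little gain.

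**Conclusion.** The point holds as a mismatch between a secondary objective and its assay schedule. With no titer between Day 0 and Day 28, the plan supports a net rise by Day 28 and the course from Day 28 to Day 180. It does not support statements about onset, early slope or the timing of seroconversion within the first 28 days, and it would miss a peak in that period. The schedule facts are certain; the effect on the peak is possible but of unknown size. Seroconversion by Day 90 and the primary infection definition in Section 2.1 are not affected.

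The timing of virus clearance rests on the reading of Table 7 given above. The remedy rests on the assumption that enough Day 14 and Day 21 serum remains after other uses. This is an inexpensive improvement, not a threat to the trial's main conclusions.

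**What to change.** 1. In Section 9.4, add PRNT50 on Days 14 and 21, run on the immunology serum already drawn. Add Day 8 as well if titers near viral clearance are wanted.
2. In Sections 9.5.3 and 9.6.2, let these values enter the peak through Day 90. Leave the present sample requirements as they are, so that no subject is newly excluded.
3. Test stored Day 14 and Day 21 serum from cohorts 1 and 2 where volume allows.
4. Also report the peak over Days 28 to 90 for all four cohorts, so that they stay comparable if early serum is short in cohorts 1 and 2.

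The cost is about 112 assays and short edits to three sections, with no new visit, blood draw or subject. If the assays are not added, reword the objective in the precis and Section 2.2 to cover titers from Day 28 onward; that costs nothing but gives up the early response.

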9.5 Per Protocol Analysis

9.5.1 Safety Data

The adverse event data will be included in the per-protocol analysis of all subjects who received an inoculation, even if one or more study visits during safety follow-up period were missed. This will assure that the largest body of safety data are included in the analysis.

9.5.2 Virology

Subjects who were enrolled through Study Day 180, even if they missed one or more visits during this time period will be included in the per-protocol analysis of viral shedding. Because there are frequent visits and an inpatient stay, missing these time-points is not expected to affect the analysis of the duration of virus shedding.

9.5.3 Immunogenicity Data

The frequency of seroconversion and peak neutralizing antibody titers will be included in the per-protocol analysis for all subjects who were enrolled through Study Day 90 and have samples from at least 2 of the following 3 time-points (Day 28, 56, 90).

9.6 Intent-to-Treat Analysis**9.6.1 Virology**

Subjects who were not enrolled through Study Day 180 but who had samples collected for ZIKV isolation will be included in the intent-to-treat analysis of viral shedding.

9.6.2 Immunogenicity Data

Subjects who did not complete Study Day 90 but did complete Study Day 28 or 56 will be included in the intent-to-treat analysis of seroconversion and peak neutralizing antibody titer.

10 PROTECTION OF HUMAN SUBJECTS**10.1 Institutional Review Boards**

The PI will be responsible for obtaining IRB approval for the study. Before the start of the study, the appropriate documents (including, but not limited to, the protocol, Investigator's Brochure, informed consent form, information sheets, and advertisements) will be submitted to the IRB for approval. A copy of the study approval (including approval of the informed consent form) is to be maintained in the investigator study document binder and a copy will be supplied to the Sponsor. During the study, the investigator is responsible for providing the IRB with all documents subject to review (e.g., protocol amendments, informed consent form updates, advertisements, and any written information that may be provided to the subject). Annual reports on the progress of the study will be made to the IRB by the investigator in accordance with IRB guidelines and government regulations.

10.2 Informed Consent

In obtaining and documenting informed consent, the investigator and study staff must comply with the applicable regulatory requirements, GCP guidelines, and ethical principles. The written informed consent form must be approved by the IRB prior to its use. A copy of the informed consent document will be given to the subject for his or her records. The subject may withdraw consent at any time during the course of the trial. The rights and welfare of the subjects will be protected by emphasizing to them that the quality of their medical care will not be adversely affected if they decline to participate in or if they withdraw from the study this study.

10.3 Risks

The risks to the subjects are minimal and are generally associated with venipuncture and ZIKV infection. These risks are outlined below. There is a potential risk of ZIKV transmission to the community by mosquito as well as by sexual transmission. In addition, questions asked regarding a subject's sexual history may make the subject uncomfortable. These questions will be asked in a private area and the subject will be made aware that they do not have to answer any

question that they do not feel comfortable answering. Subjects will be informed of the known risk of ZIKV and birth defects in the fetus. Subjects will be advised to use effective birth control methods while at risk for ZIKV infection (we will follow CDC guidelines of 8 weeks for people of childbearing potential and 12 weeks for men post-infection time of infection is defined as inoculation with challenge virus). Those of child bearing potential will also be required to use barrier contraception through study day 56 to prevent Zika transmission, in accordance with CDC guidance. Males will be advised to use barrier contraception through study day 90 to prevent Zika transmission in accordance with CDC guidance.

